### Secondary objectives:

- To evaluate the prognostic impact (in terms of DFS, BCSS and OS) of pregnancy following breast cancer diagnosis in various subgroups of *BRCA* mutated patients according to:
  - Type of *BRCA* mutation: *BRCA1* vs. *BRCA2*;
  - Hormone receptor status: positive vs. negative;
  - HER2 status: positive vs. negative;
  - Exposure to chemotherapy: prior exposure vs. no prior exposure;
  - Exposure to endocrine therapy: prior exposure vs. no prior exposure;
  - Interval between diagnosis and pregnancy:  $\leq 2$  years vs.  $> 2$  years after diagnosis;
  - Outcome of pregnancy: abortion vs. completed pregnancy;
  - Breastfeeding status: breastfeeding vs. no breastfeeding.
- To evaluate the pregnancy, fetal and obstetrical outcomes of the pregnancies following breast cancer diagnosis in *BRCA* mutated patients.
- To evaluate the safety of ART procedures following breast cancer diagnosis in *BRCA* mutated patients.

- To evaluate the impact of anticancer therapies on patients' ovarian function, in terms of incidence of treatment-induced POF and age at menopause.
- To describe baseline, tumor and treatment characteristics as well as patterns of care including access to risk-reducing surgeries in *BRCA* mutated patients.
- To evaluate the prognostic impact of baseline, tumor and treatment characteristics as well as of risk-reducing surgeries in *BRCA* mutated patients.
- To evaluate tumor infiltrating lymphocytes (TILs) in *BRCA* mutated patients.

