### 3.3. Data collection

For all consecutive eligible patients included in the study from each participating Institution, their medical records will be retrieved and anonymized data entered into a database. The following information will be collected, if available:

- 1) Baseline characteristics: body mass index; smoking habit; age at menarche; age at menopause; menopausal status at the time of breast cancer diagnosis; use of birth control pills; prior children before breast cancer diagnosis; history of spontaneous abortion; history of induced abortion; prior treatment for infertility; prior gynecological surgery and/or medical history with possible impact on fertility.
- 2) Breast cancer history: date of diagnosis; age at diagnosis; disease stage; laterality of the primary tumor; type of breast and axillary surgery; use of breast reconstruction surgery; grade; histology; tumor size and nodal status (for patients who underwent primary systemic therapy, only clinical tumor size and nodal status will be collected); hormone receptor status (estrogen and progesterone receptors); HER2 status.
- 3) Treatment of the primary tumor: timing of systemic therapy administration; use of chemotherapy (type and number of cycles); use of endocrine therapy (type and duration); use of anti-HER2 targeted therapy (type and duration); use of radiotherapy.
- 4) Survival status: any recurrence of invasive breast cancer including date of the event; any second primary breast cancer including date of the event; any second primary malignancy including date of the event; date of last follow-up and/or death; cause of death (breast cancer-related or not).
- 5) Ovarian function after chemotherapy: treatment-induced POF; age at menopause.

6) Pregnancy after breast cancer: any pregnancy including date of the event; pregnancy outcome; gestational age at delivery; any pregnancy/fetal/birth complications; breastfeeding and its duration; use and type of ART.

7) BRCA mutation: date of *BRCA* testing; type of *BRCA* mutation; use and date of breast prophylactic surgery; use and date of gynecological prophylactic surgery.

8) Additional information: diagnosis of breast cancer during pregnancy, availability of digital scanned images for TILs analysis

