## 4. STATISTICS

The achievement of pregnancy after diagnosis of breast cancer will be the criteria used to distinguish between two cohorts of patients: women with no subsequent pregnancies after breast cancer diagnosis (“non-pregnant cohort”), and women with one or more pregnancies any time after breast cancer diagnosis (“pregnant cohort”). Pregnancies could have resulted in live births, therapeutic or spontaneous abortions.

More than 2000 non-pregnant *BRCA* mutated breast cancer patients and more than 200 pregnant *BRCA* mutated breast cancer patients are expected to be included in the present study (estimated numbers, considering an incidence of pregnancy of approximately 10%).

To evaluate the prognostic impact of pregnancy following breast cancer diagnosis in *BRCA* mutated survivors, three survival endpoints will be considered in the two cohorts: DFS (as primary endpoint) BCSS (as secondary endpoint) and OS (as secondary endpoint). DFS event is defined by the occurrence of one of the following invasive events: local recurrence, distant metastases, contralateral or ipsilateral breast tumor, second primary malignancy, or death from any cause. BCSS event is defined as death from breast cancer. OS event is defined as death from any cause. For DFS, observation times of patients without the event will be censored on the date of their last contact. Using individual patient data from all patients included in the study, survival outcomes of patients in the

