pregnant cohort will be compared to those of patients in the non-pregnant cohort. To reduce the impact of selection bias (i.e. guaranteed time bias), two analyses will be performed. In the extended Cox model analysis with occurrence of pregnancy as a time-varying covariate, all eligible patients included in the study will be considered. In the “case-control” analysis, each patient in the pregnant cohort (case) will be matched with 3 patients from the non-pregnant cohort (controls). To adjust for guaranteed time bias, each patient in the non-pregnant cohort should have a disease-free interval equal to or longer than the time elapsing between breast cancer diagnosis and date of pregnancy of the matched patient in the pregnant cohort. Patients who became pregnant after the date of the DFS event will be dropped from this analysis. Patients will be also matched according to several variables including type of *BRCA* mutation (*BRCA1* vs. *BRCA2*), hormone receptor status (positive vs. negative), nodal status (negative vs. positive), and year at diagnosis ( $\pm 2.5$  years). Because all included patients are aged  $\leq 40$  years at the time of diagnosis, matching according to age will not be performed. The matching will be done centrally at the coordinating center. Two data sets will be constituted: one for the cases and one for the potential controls. Cases will be sorted randomly and matching will be done starting for the first case until the last one. For each case, all possible controls will be extracted from the data set of potential controls. If they are only 2 controls available, matching criteria will be relaxed one by one (starting from year of diagnosis, etc) until at least a third control is found. It is anticipated, given the expected low rate of cases in the full database, to reach matching for almost each case. In these analyses, all survival endpoints will be calculated from the date of pregnancy until the date of the event. In the non-pregnant cohort, survival endpoints will be calculated from the date of diagnosis, adding the time elapsing between diagnosis and pregnancy of the matched pregnant case.

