The prognostic impact (in terms of DFS, BCSS and OS) of pregnancy following breast cancer diagnosis will be then evaluated in various subgroups of *BRCA* mutated survivors according to: type of *BRCA* mutation (*BRCA1* vs. *BRCA2*), hormone receptor status (positive vs. negative), HER2 status (positive vs. negative), exposure to chemotherapy (prior exposure vs. no prior exposure), exposure to endocrine therapy (prior exposure vs. no prior exposure), interval between diagnosis and pregnancy ( $\leq 2$  years vs.  $> 2$  years after diagnosis), outcome of pregnancy (abortion vs. completed pregnancy), and breastfeeding status (breastfeeding vs. no breastfeeding).

Considering a rate of pregnancy of approximately 10%, with 2000 non-pregnant and 200 pregnant *BRCA* mutated breast cancer patients, assuming a DFS rate of 65% at 5 years in the non-pregnant cohort [21], the study will have a power of 0.83 to detect a hazard ratio of 0.75 and a power of 0.62

to detect a hazard ratio of 0.80 in favor of the pregnant cohort, at a two-sided significance level 0.05 (accrual duration 2000-2020, total study duration 2000-2030).

The rate of pregnancy following breast cancer diagnosis will be computed according to the Kaplan-Meier method. A possible increasing or decreasing trend in rate of pregnancy following breast cancer over the years will be also assessed.

The statistical analysis to evaluate the pregnancy, fetal and obstetrical outcomes of the pregnancies following breast cancer diagnosis in *BRCA* mutated survivors will be mainly descriptive and will include the following parameters:

1. Gestational age at delivery;
2. Incidence of early pre-term (< 34 weeks), late-preterm (34-36 weeks) and full-term ( $\geq$  37 weeks) pregnancies;
3. Number of pregnancies resulting in live birth and number of children born;
4. Incidence of induced and spontaneous abortion;
5. Incidence and nature of pregnancy complications (if any);
6. Incidence and nature of fetal complication and/or congenital malformations (if any);
7. Incidence and nature of obstetrical complications (if any).

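### The breastfeeding subgroup has no stated eligible population, comparator or start of follow-up, so its DFS contrast can be biased by bilateral mastectomy in one direction and by timing in the other

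*Combined protocol and SAP*

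**What the plan says.** The secondary objectives (Section 2) list "Breastfeeding status: breastfeeding vs. no breastfeeding" as one of the subgroups in which the prognostic impact of pregnancy is studied for DFS, BCSS and OS. Section 4 repeats it: "and breastfeeding status (breastfeeding vs. no breastfeeding". Neither place gives a denominator.

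The surrounding text matters in five ways:

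- **Cohort.** Section 4 says of the pregnant cohort: "Pregnancies could have resulted in live births, therapeutic or spontaneous abortions".
- **Neighbouring subgroup.** Section 4 lists "outcome of pregnancy (abortion vs. completed pregnancy" as a subgroup of its own and does not link it to breastfeeding.
- **Endpoint.** A DFS event is any of "local recurrence, distant metastases, contralateral or ipsilateral breast tumor, second primary malignancy, or death from any cause" (invasive events).
- **Clock.** After describing the matched analysis, Section 4 says that "all survival endpoints will be calculated from the date of pregnancy until the date of the event". For non-pregnant controls the diagnosis-to-pregnancy time of the matched case is added.
- **Data.** Section 3.3 collects pregnancy outcome, type of breast surgery, "breastfeeding and its duration" and "use and date of breast prophylactic surgery". Breast surgery is not among the matching factors. The multivariate Cox models in Section 4 come without a covariate list.

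**The concern.** In a two-level variable with no eligibility rule, everyone who did not breastfeed falls into the second level. That level then mixes women with no live birth, women with a live birth but no remaining breast, and women who could have breastfed and did not. Only the third group is a proper comparator.

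The second group is the one that distorts DFS. These women cannot have the exposure, and they have little tissue in which a contralateral or ipsilateral breast tumor can arise. Inability to breastfeed is therefore tied to a lower risk of the primary endpoint, and nothing in the plan breaks that tie.

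The Background (Section 1) gives the absence of information on breastfeeding in these patients as one reason for the study. The result may therefore be used in counselling, and the contrast should not partly measure surgery or the timing of events.

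**Working it through.** The documents give no figure for this subgroup; the power statement in Section 4 covers only the main comparison and is not used here. The one usable figure is the assumed 65% DFS at 5 years in the non-pregnant cohort.

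**Step 1: hazard.** With a constant hazard, h = -ln(0.65)/5 = 0.4308/5 = 0.0862 per year, or 8.6%/year. Using it for women after a pregnancy is itself an assumption.

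**Step 2: mastectomy effect alone, with no true effect of breastfeeding.** Let c be the yearly rate of new breast primaries in women with breast tissue and s the share of non-breastfeeders with no remaining breast. Assume that bilateral mastectomy removes 90% of c. Breastfeeders have hazard h and the pooled comparator averages h - s × 0.9 × c, so

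HR = h / (h - s × 0.9 × c).

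| s | c | s × 0.9 × c | HR at h = 0.0862 |
|---|---|---|---|
| 0.20 | 0.01 | 0.0018 | 0.0862/0.0844 = 1.02 |
| 0.35 | 0.02 | 0.0063 | 0.0862/0.0799 = 1.08 |
| 0.50 | 0.03 | 0.0135 | 0.0862/0.0727 = 1.19 |

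The values of s, c and the 90% are assumptions.

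**Step 3: simulation of both mechanisms, again with no true effect.** Assumptions: 25% of pregnancies end in abortion; 15-50% of women have bilateral mastectomy; new breast tumors are 20-50% of DFS events and are cut by 90% after mastectomy; half of the women able to breastfeed do so; follow-up is 6 years; breastfeeding status is settled 0.75 years after the date of pregnancy. Where timing bias is included, an event before that point rules out breastfeeding unless stated otherwise.

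| Analysis | Null DFS HR, breastfeeding vs none |
|---|---|
| All non-breastfeeders pooled, timing bias switched off | 1.04-1.41 |
| All pooled, clock from pregnancy | 0.84-1.17 (below 1 in 7 of 9 settings) |
| All pooled, clock from delivery | 1.06-1.36 |
| Abortions and bilateral mastectomies excluded, clock from pregnancy | 0.73-0.77 |
| Same exclusion, clock from delivery | about 1.0 (0.96-1.04, simulation noise) |

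At 30% mastectomy and a 30% breast-event share, the pooled HR from pregnancy is 1.12, 1.02 or 0.90 when 0%, 50% or 100% of women with an event before delivery are prevented from breastfeeding. The corresponding restricted HRs are 0.99, 0.88 and 0.76.

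**Step 4: the other components.** With timing bias off and no mastectomy, pooling abortions gives HR 1.00 if abortion has no prognostic effect. It gives 1.08 if the HR for abortion is 0.80 and 0.91 if it is 1.25. For an outcome that mastectomy does not affect, pooling gives 0.99.

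**The case against.** The strongest reply is that the plan is silent rather than wrong. No sentence says that abortions or mastectomies are coded as no breastfeeding. Because abortion versus completed pregnancy is listed immediately before, limiting breastfeeding to completed pregnancies is a natural reading. This stands as far as it goes: the pooling is the literal reading, not a stated rule. But even the kinder reading leaves women without a remaining breast in the comparator.

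Second, Section 4 speaks of the effect of pregnancy within subgroups, so breastfeeders might be compared with their non-pregnant controls. The plan does not say. The problem would change form but remain, since breastfeeders necessarily retain a breast while controls are not matched on breast surgery.

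Third, the likely shift is small against the noise. With about 200 pregnant women expected, and assuming 60 events split evenly, the 95% confidence factor for a subgroup HR is exp(1.96 × √(4/60)) = 1.66. This is fair, and it limits the severity. It does not justify leaving the population undefined.

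Fourth, the multivariate models could include surgery, and risk-reducing surgery is studied as its own objective. Neither is tied to this subgroup.

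A reader might also infer that abortions make breastfeeding look harmful. The documents do not support that: the Background reports no impact of abortion on outcome in a cited retrospective cohort, and on that basis pooling abortions is neutral. That study is cited before the text turns to BRCA carriers, so some uncertainty remains.

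**Conclusion.** The point holds as a gap in definition with a specific route to bias. Taken literally, the split ties inability to breastfeed to lower DFS risk. With no true effect, that alone gives a DFS HR of about 1.02-1.19 at the document-based hazard, under the assumed rates in Step 2.

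Three stronger readings are not supported:

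- **That breastfeeding will look harmful.** The clock starts at the date of pregnancy, before breastfeeding can occur. This favours breastfeeding and outweighs the mastectomy effect in most simulated settings where every event before delivery prevents breastfeeding. The net direction is uncertain.
- **That the bias reaches an HR near 1.4.** At an assumed 5%/year hazard the formula gives up to 0.05/(0.05 - 0.0135) = 1.37, but this needs new breast primaries to be 0.03/0.05 = 60% of all DFS events, together with half of the comparator having no breast. The simulated 1.41 likewise needs the top of both ranges.
- **That all survival endpoints are affected.** The mastectomy mechanism concerns DFS. BCSS and OS are little affected by it unless mastectomy changes mortality.

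Restriction alone would not suffice. Without a change of time zero it leaves a null HR of about 0.73-0.77 if every event before delivery prevents breastfeeding. Moving the clock alone leaves 1.06-1.36. Only the two together return about 1.0.

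**What to change.** In the secondary objectives and in Section 4:

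1. Limit the breastfeeding analysis to women with a live birth who had at least one breast at delivery. Where breast status or its date is incomplete, adjust for bilateral mastectomy instead.
2. Report women with bilateral mastectomy and women whose pregnancy ended in abortion separately, not as non-breastfeeders.
3. Start follow-up at delivery, or at a stated landmark after it, among women still event-free.
4. State whether the comparator is non-breastfeeders or matched non-pregnant controls. If controls are used, apply the same mastectomy restriction or adjustment to them.

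The change is to the analysis text and uses fields already listed in Section 3.3. Those fields are collected only where available, and the list gives no side for prophylactic surgery and no date for therapeutic surgery. Breast status at delivery may therefore not be derivable for everyone, which is why the adjustment option is needed. The price is a smaller subgroup and a wider confidence interval.

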Number of patients	More than 2000 non-pregnant BRCA mutated breast cancer patients and more than 200 pregnant BRCA mutated breast cancer patients (estimated numbers, considering a rate of pregnancy of approximately 10%).
Eligibility criteria	
Inclusion criteria:
 
 
- Diagnosis of invasive breast cancer between January 2000 and December 2020;
 
- Breast cancer diagnosis at the age of <math>\leq 40</math> years;
 
- Known presence of germline BRCA pathogenic variant.
 
 
Exclusion criteria:
 
 
- Known BRCA mutation with no diagnosis of invasive breast cancer;
 
- Diagnosis of ovarian cancer or other malignancies with no history of invasive breast cancer;
 
- Diagnosis of hereditary or familial invasive breast cancer without BRCA mutation or with BRCA genes not tested;
 
- Diagnosis of invasive breast cancer with germline BRCA variants of unknown significance.
 

Design of the trial	Retrospective multicenter hospital-based study

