
Statistics
	
The achievement of pregnancy after diagnosis of breast cancer will be the criteria used to distinguish between two cohorts of patients: women with no subsequent pregnancies after breast cancer diagnosis (“non-pregnant cohort”), and women with one or more pregnancies any time after breast cancer diagnosis (“pregnant cohort”). To evaluate the prognostic impact of pregnancy following breast cancer diagnosis in BRCA mutated survivors, three survival endpoints will be considered in the two cohorts: disease-free survival (DFS, as primary endpoint) breast cancer specific survival (BCSS, as secondary endpoint) and overall survival (OS, as secondary endpoint). To reduce the impact of selection bias (i.e. guaranteed time bias), two analyses will be performed. In the extended Cox model analysis with occurrence of pregnancy as a time-varying covariate, all eligible patients included in the study will be considered. In the “case-control” analysis, each patient in the pregnant cohort (case) will be matched with 3 patients from the non-pregnant cohort (controls). Each nonpregnant control should have a disease-free interval equal to or longer than the time elapsing between breast cancer diagnosis and date of pregnancy of the matched pregnant case. Patients who became pregnant after the date of the DFS event will be dropped from this analysis. The other matching factors will be year at diagnosis (<math>\pm 2.5</math> years), nodal status (negative vs. positive), hormone receptor status (positive vs. negative), and type of BRCA mutation (BRCA1 vs. BRCA2). Because all included patients are aged <math>\leq 40</math> years at the time of diagnosis, matching according to age will not be performed. The matching will be done centrally at the coordinating center. The prognostic impact (in terms of DFS, BCSS and OS) of pregnancy following breast cancer diagnosis will be then evaluated in various subgroups of BRCA mutated survivors. Pregnancy rate will be computed according to the Kaplan-Meier method.

--------------------------	---

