## 2. STUDY OBJECTIVES

### Primary objectives:

- To evaluate the prognostic impact of pregnancy following breast cancer diagnosis in *BRCA* mutated patients. The following survival endpoints will be considered: disease-free survival (DFS, as primary endpoint), breast cancer specific survival (BCSS, as secondary endpoint) and overall survival (OS, as secondary endpoint).
- To evaluate the rate of pregnancy following breast cancer diagnosis in *BRCA* mutated patients.

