In order to conduct the evaluation of TILs in this cohort, there will be no need for new cutting/preparation of tumor slides. The evaluation will be conducted on one archived diagnostic tumor-containing slide stained with hematoxylin and eosin representative of the primary tumor. The TILs scoring will be performed centrally. If available, anonymized digitally scanned images of the diagnostic hematoxylin and eosin-stained slide should be sent via email to [name] ([[contact]](mailto:[contact])) at University of Padova-Istituto Oncologico Veneto (Padova, Italy). The University of Padova-Istituto Oncologico Veneto will take care of costs related to TILs scoring and storage support (hard disk). The evaluation will be performed according to the TILs working group recommendations [24].

Patients demographic, clinical and pathologic baseline characteristics will be compared by pregnancy status using chi-square test or Fisher Exact test for categorical variables and Wilcoxon rank-sum test or t-test for continuous variables, as appropriate.

Dichotomous outcomes will be compared using univariate and multivariate logistic regression models. Time-to-event outcomes will be estimated and plotted using Kaplan-Meier methods. Survival rates will be compared using log-rank test and Cox proportional hazards models for univariate and multivariate analysis, respectively.

All tests will be two-sided and p-values of  $< 0.05$  will be considered statistically significant. All

analyses will be performed using standard available statistical programs.

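### The pregnancy rate, a primary objective, is to be estimated by Kaplan-Meier with no rule for death before pregnancy; with deaths censored, it modestly exceeds the cumulative incidence at the same time point

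*Combined protocol and SAP*

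**What the plan says.** Section 2 lists the pregnancy rate among the primary objectives: "To evaluate the rate of pregnancy following breast cancer diagnosis in" women with a *BRCA* mutation. The estimator is named in Section 4, "The rate of pregnancy following breast cancer diagnosis will be computed according to the Kaplan-Meier method", and again in the Statistics row of the Synopsis, "Pregnancy rate will be computed according to the Kaplan-Meier method". Section 4 adds that a trend over the years will be assessed, and gives a general rule: "Time-to-event outcomes will be estimated and plotted using Kaplan-Meier methods".

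The only censoring rule is for another endpoint: "For DFS, observation times of patients without the event will be censored on the date of their last contact". No section mentions a competing event, a cumulative incidence method, a time point for the rate, or what happens to a woman who dies before any pregnancy.

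The only pregnancy figure is a planning value of about 10%. The Synopsis calls it a rate ("estimated numbers, considering a rate of pregnancy of approximately 10" per cent). Section 4 calls it an incidence ("estimated numbers, considering an incidence of pregnancy of approximately 10" per cent) and, in the power statement, a rate again ("Considering a rate of pregnancy of approximately 10%, with 2000 non-pregnant and 200 pregnant").

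**The concern.** A woman who has died cannot become pregnant. Kaplan-Meier with deaths censored treats her as if she would have gone on to conceive at the same rate as the women still under observation. One minus the curve (1-KM) then describes pregnancy in the hypothetical absence of death, whereas the objective as worded invites the reader to see the share of women who become pregnant.

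The direction is a mathematical property. At any given time 1-KM cannot lie below the cumulative incidence, and it lies above it once deaths without pregnancy have been followed by later pregnancies among the remaining women. Deaths after a pregnancy, or after the last pregnancy in the cohort, add nothing to the gap. At stake is the value and meaning of one primary estimate.

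**Working it through.** **Inputs from the documents.** Planned cohorts of 2000 non-pregnant and 200 pregnant women; accrual 2000-2020; 5-year DFS of 65% in the non-pregnant cohort, with death from any cause counted as a DFS event (all Section 4).

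**The plan's own figure.** The 10% is a planning assumption with no calculation behind it. 200/2200 = 9.1% and 200/2000 = 10%; both fit the word approximately.

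**Assumptions.** The documents give no overall survival (OS), reporting horizon or timing of pregnancies. I take a true 10-year cumulative incidence (CIF) of 10% and 10-year OS of 95, 90, 80, 75 and 65%. The constant death hazard is m = -ln(OS10)/10. In each pattern the pregnancy hazard h is solved so that CIF(10) = 10%.

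- Pattern A, pregnancies only in years 1 to 6: CIF(10) = exp(-m) × h/(h+m) × [1 - exp(-5(h+m))]; 1-KM = 1 - exp(-5h). Section 1 says that the window for pregnancy may be narrow but gives no years, so 1 to 6 is my choice.
- Pattern B, constant pregnancy hazard: CIF(10) = h/(h+m) × [1 - exp(-10(h+m))]; 1-KM = 1 - exp(-10h).
- Pattern A2, as A but with no deaths in the first 2 years and the same 10-year OS: m2 = -ln(OS10)/8; CIF(10) = [1 - exp(-h)] + exp(-h) × h/(h+m2) × [1 - exp(-4(h+m2))]; 1-KM = 1 - exp(-5h).

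**Worked case, A at OS 80%.** m = 0.02231 and h = 0.02285. CIF = 0.9779 × 0.5060 × 0.2021 = 0.100. 1-KM = 1 - exp(-0.1142) = 10.80%, a gap of 0.80 points.

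**10-year 1-KM when the true cumulative incidence is 10%:**

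| 10-year OS (assumed) | A | B | A2 |
|---|---|---|---|
| 95% | 10.18% | 10.25% | 10.10% |
| 90% | 10.37% | 10.53% | 10.21% |
| 80% | 10.80% | 11.13% | 10.44% |
| 75% | 11.03% | 11.47% | 10.57% |
| 65% | 11.58% | 12.25% | 10.85% |

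At 5 years the gap runs from about 0.1 to 1.1 points in A (8.23% against 8.10%, up to 9.38% against 8.26%). In B it runs from about 0.1 to 0.6 points (5.27% against 5.20%, up to 6.33% against 5.70%).

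**Against sampling error.** In simulations (1000 per scenario, 2200 women, uniform accrual 2000-2020, assumed cut-off 2022) the standard deviation of 10-year 1-KM was 0.70 to 0.89 points. From OS 95% to 65%, the gap was 0.26, 0.51, 1.11, 1.41 and 1.98 standard errors in A, and 0.33, 0.68, 1.51, 1.84 and 2.53 in B. The Aalen-Johansen estimate averaged 9.96% to 10.02% throughout.

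**Consistency with the plan.** Because DFS counts every death, 5-year OS in the non-pregnant cohort cannot be below 65%. The assumed range implies 5-year OS of 97.5% to 80.6%, well above that floor.

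**Comparator.** Under the same accrual and cut-off, the expected crude share of women with a pregnancy is 9.2-9.3% in A. In B it is 11.6, 11.4 and 11.2% at OS 95, 90 and 80%, which is above the 10-year 1-KM there. In A at OS 95%, 1-KM exceeds the crude share by 10.18 - 9.22 = 0.96 points, of which only 0.18 comes from censored deaths; the rest is short follow-up. The crude share is therefore not a yardstick for this problem; cumulative incidence at the same time is.

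**The case against.** The strongest reply is that Kaplan-Meier is a legitimate choice here. The document history records that Amendment 1 moved this objective from an incidence to a rate analysed by Kaplan-Meier, so a time-to-event quantity was chosen on purpose. One minus that curve is a valid description of pregnancy if deaths were removed, and the 10% is a planning input, not a definition of the result. This stands in part: the estimator is not wrong in itself. But nothing says that the no-death quantity is the target, and the amendment supplies no rule for deaths.

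A second reply is that the size depends on inputs that the documents do not contain. That is correct. Eligibility requires a known *BRCA* variant, so some early deaths may never enter the cohort, and pattern A2 shows the gap then roughly halves. The direction does not depend on these inputs.

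Three stronger readings are tempting but not supported:

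- A reader might infer that the result will overshoot the planned 200 of 2200. That share mixes unequal follow-up and can lie on either side of 1-KM.
- A reader might take the DFS assumption as mortality. With 65% alive at 5 years and constant hazards, 10-year 1-KM would be 14.75%. But DFS also counts recurrences and second cancers, so this is only an outer bound.
- A reader might infer that the DFS comparison or its power is compromised. Neither uses the pregnancy rate estimate.

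**Conclusion.** The point holds as a gap in the definition of a primary estimate. The plan names one estimator and leaves death before pregnancy and the time horizon unstated. Used in the standard way, that estimator overstates the cumulative incidence of pregnancy at the same time.

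The effect is modest: about 0.1 to 2.3 points on a true 10% at 10 years across all the assumed patterns, and below one standard error in patterns A and B when 10-year OS is 90% or higher. Because it is systematic, more patients would not remove it. The size rests on assumed survival and assumed timing of pregnancies and deaths; the direction and the missing rule do not. The plan ties no named test or power statement to the rate, so the harm is confined to the reported figure and how it is read. It should be fixed, but it does not threaten the study's main comparison.

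**What to change.** In the Statistics row of the Synopsis and in Section 4, replace the sentence on the pregnancy rate with wording such as:

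*The rate of pregnancy is the cumulative incidence of first pregnancy after breast cancer diagnosis at 5 and 10 years, estimated by the Aalen-Johansen method with death before any pregnancy as a competing event. Women alive without a pregnancy are censored at last contact.*

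The 5 and 10 years are examples; some horizon must be stated, because a cumulative incidence without one is a curve and not a rate. In pattern B the same process gives 5.2-5.7% at 5 years and 10% at 10 years. Kaplan-Meier may be kept as a secondary figure, labelled as pregnancy in the hypothetical absence of death. If the sponsor wants that quantity as primary, Section 2 should say so.

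The cost is two sentences and a routine estimator. Dates of pregnancy and death are already on the collection list in Section 3.3. The downside is a slightly lower reported rate and a little extra analysis. The change does not deal with survival up to *BRCA* testing, which is a separate matter.
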